8.1 Enrolment/screening

Screening of suitable participants will be undertaken in two phases. The first phase will be conducted via an online screening questionnaire. The second phase will combine a non-invasive technique (wrist actigraphy and sleep diary) for the at-home measurement of normal sleep/wake cycles and an at home clinical assessment with the study research team.

Phase 1: Online Screening

Online screening procedure is described in 12.3

All participants who attempt stage 1 of screening (i.e. receive a unique login, see 13.2.2) will be assigned with a sequential screening number (i.e. S1, S2 etc)

Phase 2: Home Screening

The home screening procedure is described in 12.3.1

If a potential participant is deemed suitable by the online screening procedure they will be contacted by the study coordinator and a face-to-face screening appointment at their home will be arranged. For 7 days preceding this appointment they will wear an Actiwatch 2 and asked to fill out a sleep diary. Participants will be sent instructions with the device and diary via courier. Actigraphy will be visually checked to ascertain whether the participant has a normal 24 sleep/wake cycle and biologically sufficient sleep (at least an average of 5.5 hours per 24 hours). Sleep diaries will also be kept to correlate with actigraphy data.

At the face-to-face screening at home, participants will have audiometry and those with impaired hearing will be excluded.

If a participant is willing and eligible they will then have the study fully explained to them and will be given the opportunity to ask questions before they give written informed consent to enrol in the study at this visit. They may also make that decision later and return informed consent documents via email, post or in person

8.2 Baseline, 3 months and 6 month home visits

Eligible participants who have given informed consent will have a baseline visit scheduled during which time they will complete a range of clinical assessments as described in Table 1.

Outcome measures will be collected at 3 and 6 month home visits. These visits will be conducted at a convenient time for the participant. Prior to the 3 and 6 month outcome assessment the participant will be sent an Actiwatch 2 to wear for two weeks prior to the visit. They will also have an overnight polysomnography (sleep study) performed. The research assistant will visit the home in the evening to connect the leads for the study. They will also provide instructions to the participants. The research assistant will return early the next day to collect the equipment.

8.3 Infrasonic or Sham speaker installation and monitoring

The acoustic engineer will schedule a visit to the home soon after baseline testing has been completed. At this visit, either infrasonic or sham speakers will be installed into the bedroom of the participant. In addition to the 4 x 600mm cube speakers we will place a monitoring box and 2 microphones in the bedroom.

The acoustic engineer is unblinded and will advise participants that if they have any concerns about the speakers that they should contact him directly and not discuss this with other members of the team who do not know what type of speaker is installed in the bedroom. Additionally, the participants will be informed that their electricity bill may increase and that they will be reimbursed for this expense. Again, this is to be discussed with the unblinded acoustic engineer who installed the speakers and not any other member of the team.

The acoustic engineer will arrange regular visits to the home of participants to check that they speakers are performing as designed and that the monitoring equipment is collecting infrasonic or sham sound exposure information. These visits will be weekly in the first month, then monthly for the next five months or as required. He will download data and bring this back to Woolcock Institute for secure storage.

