5.2 Exclusion criteria

1. Rotating shift worker
2. Planning to be away from home for more than a month during the study period

3. Major psychiatric disorders
4. Use of any hypnotic medications or other medications that interfere with sleep within the last month
5. Breastfeeding, pregnant or attempting to become pregnant women in the household
6. Young children (under 5 years) living in the home

6. Study Interventions

Participants that meet the eligibility criteria will be randomised to either:

- 1) simulated wind turbine sound at 93dB Pk (infrasound, test exposure)
- 2) absence of sound (sham, control exposure).

Four 600mm x 600mm cube speakers (photo below) will be installed in the bedroom of each participant. For participant convenience, these speakers can be placed in variable configurations within the participant's bedroom. The speakers are wired together and are powered by a single cord that plugs into a domestic power point.

In addition to the speakers there will be two microphone stands with microphones placed in the bedroom. Neither microphone will collect sound content or conversation, but they will collect the sound level in decibels of 1) infrasound and 2) audible sound.

The speakers and microphones will operate continuously over the six month period of the study. By agreement with the participant, the acoustic engineer will schedule regular visits to the home to assess the correct functioning of the equipment. These visits may be up to weekly in the first month of operation and then monthly or as required for the remaining five months of operation. All participants will be reimbursed for expenses associated with the use of electricity to run the speakers. The acoustic engineer will be unblinded to group allocation and will be the contact point for participants who want to discuss anything regarding the speakers, microphones, electricity consumption or other exposure related query, thus ensuring the participant and clinical assessment staff remain blinded to group allocation.

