11.2. Blinding

Expectations on the part of participants and investigators may influence the effect of the exposure (infrasound) and, more particularly, may influence the measurement of those effects, especially the subjective (self-reported) outcomes. To avoid the potential for this measurement bias, it is important that both participants and the investigators who are measuring outcomes are blinded to the intervention group. Fortunately, as infrasound is, by definition, inaudible, this is readily achieved by the use of a sham device that appears the same as the infrasound device, but which does not produce any sound. Only the unblinded acoustic engineer will have knowledge of the exposure and they will never disclose this group allocation to the participants or staff/investigators who interact with participants.

12. Methods: Description of study procedures

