15.1 Data monitoring

Because infrasound like this has not been used in experiments of longer than 2 hours duration a Data Safety Monitoring Board has been convened. The DSMB will oversee participant safety in both the laboratory study (Protocol No X16-0073 & HREC/16/RPAH/91) and this community based study by reviewing unblinded accumulated safety data pertaining to infrasound.

16. Adverse Events Reporting

Collection of adverse events will occur throughout the study.

Serious adverse events (SAE) are defined as any untoward medical occurrence that:

- Results in death
- Is an immediately life-threatening condition
- Requires hospitalisation or prolongs hospitalisation
- Results in persistent or significant disability/incapacity
- Is a congenital anomaly/birth defect
- Results in any other important medical condition.

The Ethics Committee will be notified of any SAE within 72 hours.

17. Auditing

The study will not be externally audited

18. Ethics and dissemination

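### Sections 6 and 8.3 send all speaker-related concerns to the unblinded engineer without separating out health complaints, and section 16 states no route from the engineer to adverse-event recording

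*Protocol*

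**What the plan says.** Section 8.3 describes what the engineer tells participants when the speakers are installed: "if they have any concerns about the speakers that they should contact him directly and not discuss this with other members of the team". The team members meant are those who do not know which type of speaker is in the room. Electricity costs are dealt with separately in the same paragraph, so the instruction is not confined to billing.

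Section 6 sets the scope more widely. The engineer is the contact for "anything regarding the speakers, microphones, electricity consumption or other exposure related query", and the stated purpose is "thus ensuring the participant and clinical assessment staff remain blinded to group allocation". The same section confirms that "The acoustic engineer will be unblinded to group allocation". Section 11.2 bars him from revealing the arm: "they will never disclose this group allocation to the participants or staff/investigators who interact with participants". That bar covers allocation only. It neither forbids nor requires passing on what participants tell him.

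On safety, section 16 says "Collection of adverse events will occur throughout the study" and "The Ethics Committee will be notified of any SAE within 72 hours". It names no collector and no method. Section 15.1 sets up a DSMB to review unblinded accumulated safety data. The schedule in Table 1 has no row for adverse events.

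**The concern.** The trial asks whether the exposure disturbs sleep, annoys people or produces the symptoms attributed to wind turbines, and it recruits people selected for noise sensitivity. A participant who thinks the speakers are causing headaches has, in ordinary language, a concern about the speakers. Someone following section 8.3 to the letter would tell the engineer and would not tell the clinical team.

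Two things are then at stake. The first is capture: no text obliges the engineer to record the complaint or hand it on. The second is handling: the first response comes from a person who knows the arm, and no common script is required. This matters more than usual here because section 15.1 gives as the reason for having a DSMB that infrasound of this kind had not been used experimentally for longer than 2 hours, whereas section 6 has the equipment running continuously for six months.

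**Working it through.** No sample-size, power or error-rate figure is involved. The check is a comparison of sections, plus two simple counts.

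**1. Does the instruction reach health complaints?** It does not mention symptoms, illness or adverse events, so it does not expressly cover them. Nothing excludes them either, and section 6's wording on other exposure-related queries is open-ended. A reasonable participant could read it as covering a symptom blamed on the speakers.

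**2. Is there a stated handover?** I looked in sections 6, 8.3, 11.1, 11.2, 15.1 and 16 and in Table 1. None gives the engineer a duty to record or forward a health remark. Section 11.1 blinds staff who collect clinical outcomes but does not say who collects adverse events. Section 15.1 does not say how safety data reach the DSMB.

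**3. Scheduled contacts during exposure.**
- Engineer (section 8.3): 4 weekly visits in month 1 + 5 monthly visits = 9. Section 6 makes the first-month visits at most weekly, so this is up to about 9. Both sections also allow visits as required.
- Blinded outcome assessments (section 3): 2, at three and six months.

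The engineer can therefore be the more frequent scheduled contact as well as the designated one.

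**4. Would the scheduled questionnaires pick up what the engineer hears?** Section 12.5 and Appendix B collect symptoms at baseline, 3 and 6 months. Their time frames are short:
- symptom visual analogue scales and Noise Annoyance Scale: current state;
- DASS-21: past week;
- Insomnia Severity Index: last 2 weeks.

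Taking six months as 6 × 52/12 = 26 weeks, two administrations of DASS-21 look back over 2 × 1 = 2 weeks (2/26, about 8%), and two of the Insomnia Severity Index over 2 × 2 = 4 weeks (4/26, about 15%). A complaint that arises in month 1 and resolves, or that leads to withdrawal before month 3, may not appear on any of these four instruments. Complaints that persist to a visit can appear there.

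**5. What does not pass through the engineer?** The questionnaires are completed by the participant whether or not the speakers are blamed. WASO comes from polysomnography analysed in a single core laboratory (section 12.7).

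**The case against.** The strongest case on the other side has four parts.

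- **Nothing says that complaints bypass adverse-event collection.** A reader might infer that they do. The documents do not support this: section 16 requires collection throughout and does not rule out the engineer as a source. What stands is narrower, namely that no route is stated and the instruction to participants points away from clinical staff.
- **Keeping speaker queries from assessors is a legitimate blinding measure.** A reader might infer that the rule does nothing for blinding, since a complaint does not prove which device is installed. That goes too far. Section 11.2 is concerned with expectations, and an assessor's guess can influence measurement even if it is wrong. The introduction also says that infrasound at a high enough level can be sensed, whereas the sham emits nothing, so some complaints could be informative. This objection stands in full for equipment and electricity queries.
- **Other safety routes exist.** Section 6.1 provides for checking that a participant who stops responding has not had an adverse event, and section 23 for medical follow-up if harm occurs. These help, but both start once non-response or harm has come to the team's notice, and neither picks up a complaint that was made only to the engineer.
- **The information sheet and consent form may name a contact for health problems.** They were not available to me, so I do not claim that no such contact exists. A contact named there would still sit beside a contrary instruction in section 8.3.

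**Conclusion.** The concern holds as a fault in routing and handover. Sections 6 and 8.3 do not distinguish equipment queries from health complaints, and section 16 provides no path from the engineer to the adverse-event record or the DSMB. The data mainly exposed are between-visit safety reports, which may be under-recorded or first handled with knowledge of the arm. An indirect effect on later self-reports is possible if reassurance differs by arm, but nothing in the protocol shows that it would.

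A reader might go further and infer that the symptom and annoyance outcomes are biased. The protocol does not support that: those outcomes are scheduled instruments outside the engineer's route, as is WASO.

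The number of complaints affected cannot be derived. The conclusion assumes that some participants will take a symptom blamed on the speakers to be a concern about the speakers. This is protocol content on trial conduct, not detail that would normally be left to a statistical analysis plan.

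**What to change.** Reconcile sections 6, 8.3 and 16.

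1. Keep equipment and electricity queries with the engineer, under one written script used identically in both arms.
2. State in section 8.3, and in what participants are told, that the instruction does not cover symptoms or health concerns. These should be reported to the study team whether or not the participant blames the speakers, preferably to an existing team member who does not perform the outcome assessments.
3. Have the engineer write down any health remark verbatim and forward it, without allocation, to the adverse-event log. Section 16 should name this route, say who receives the reports and state that they form part of what the DSMB reviews.

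The cost is a few sentences and a short script. The small downside is that some blinded staff may hear complaints about the speakers; routing these to someone who does not assess outcomes limits it. The existing protection of the blind for equipment matters is unchanged.

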8.4 Reimbursement

Participants will be fully reimbursed for the additional cost of electricity for running the speakers and microphones. We anticipate that this amount will be in the range of \$60 to \$120. We will offer a payment of \$1,000 to cover electricity and the inconvenience of having the speakers in the home and participating in the testing for all participants involved in this study.

9. Sample size

From previous studies, the between-subject standard deviation in wake after sleep onset (WASO) is conservatively estimated at 20 minutes. Most trials of treatments for insomnia, for instance, regard a change of 15 minutes or more in WASO as being clinically meaningful. A sample size of 120 participants (which includes allowance for 22 dropouts) will have 85% power to detect a 0.25 effect size (Cohen's f).

10. Recruitment

Number and source of participants

The target number of participants is 120. This will provide 60 participants in the infrasonic group and 60 participants in the sham group.

Participants will be found by public advertising in local newspapers, community radio, television media and social media through the Woolcock website and its database of

research volunteers which will direct all volunteers to the online screening website (Appendix A).

11. Methods: Assignment of interventions

11.1 Randomisation

Participants will be randomised to either infrasound or sham through the use of a pre-programmed randomization plan from <http://www.randomization.com>. All study personnel who collect clinical outcomes from participants will be blinded to group allocation. The only unblinded personnel will be the acoustic engineer and two senior chief investigators who independently check that the randomisation schedule is being implemented as designed.

11.2. Blinding

Expectations on the part of participants and investigators may influence the effect of the exposure (infrasound) and, more particularly, may influence the measurement of those effects, especially the subjective (self-reported) outcomes. To avoid the potential for this measurement bias, it is important that both participants and the investigators who are measuring outcomes are blinded to the intervention group. Fortunately, as infrasound is, by definition, inaudible, this is readily achieved by the use of a sham device that appears the same as the infrasound device, but which does not produce any sound. Only the unblinded acoustic engineer will have knowledge of the exposure and they will never disclose this group allocation to the participants or staff/investigators who interact with participants.

12. Methods: Description of study procedures

12.1 Informed consent

Each potentially eligible participant will be informed of the study's objectives and overall requirements by the lead study coordinator or one of the principal investigators using the participant information sheet and informed consent form, and they will be provided with a copy of the forms. If the participant is willing to participate in the study, they will be requested to give written, witnessed, informed consent.

12.2 Simulated infrasound waveform and sham infrasound

The infrasound attributable to wind turbines will be simulated using a 0.8 Hz trapezoidal-shaped waveform with 16 harmonics (Figure 2). Conventional audio systems are not capable of generating sound levels at 0.8 Hz. Therefore, a purpose built apparatus will be utilised (Figure 2).

[figure not shown]

Figure 2. The Walker Speaker Boxes and the Simulated Spectrum

The apparatus generates the required waveform using three 18" sub-woofer drivers in a timber enclosure. Four 18" JBL high power sub-woofers will be used, each constructed separately in timber boxes with integral power amplifiers. . The separating gap between the enclosures is open on all four sides of each infrasound cube (i-cube) from which the infrasound pressure waveform will be emitted. The 4x 600mm i-cubes will be placed in convenient corner locations within master bedroom. The i-cubes will be electronically connected by cable to enable the infrasound waveform signature to be fed to all four speakers simultaneously. Sham units will be constructed to appear identical to the active (infrasound-emitting) i-cubes, but will not emit any audible sound or infrasound.

12.2.1 Monitoring infrasound exposure

Sound level in the master bedroom will be measured by a low frequency microphone (Fig 3) type G.R.A.S. 40AZ which is a ½" Pre-polarised Free-Field Microphone connected to a G.R.A.S. Type 26CG ¼" Low Frequency CCP Preamplifier. The G.R.A.S. 40AZ microphone has a frequency response of 0.5Hz to 20 kHz (+/- 2dB) which encompasses the range of the study. As well, a G.R.A.S. 12AL 1-Channel CCP Power Module, custom built 50Hz low pass filter/amplifier and Graphtec GL220 data logger with USB hard drive will be utilised for data acquisition. The infrasound will be recorded on the USB hard drive for post processing. Peak sound levels will be measured for each 15 minute interval. All equipment will be certified as conforming to appropriate international standards at the NATAcoustic NATA registered laboratory in Sydney. Only the unblinded acoustic engineer will have access to this data.

Figure 3. Microphone stand with infrasound and audible sound microphones

12.3 Online screening website

Through various recruitment strategies participants will be referred to an online website to register their interest (Appendix A) where they will be asked to register with their details (Name, Phone number, Email address and Postcode) and in return, participants will be sent a unique login and instructions to complete an online questionnaire for this study that will be used as a tool to help screen and phenotype participants. The online questionnaire is a series of questionnaires (Appendix B & C) asking about general health, medication use and medical history, lifestyle and sleeping patterns. Furthermore, participants will answer various questionnaires regarding their psychological wellbeing which will further assist in the decision determining the suitability for each participant. Some questionnaires will be automatically scored using standardised scoring algorithms that will help in excluding

participants who are unsuitable and flagging participants who require a decision to be made by members of the research team. Participants will be asked to give consent before beginning the questionnaire for screening online and, if eligible, at a home visit.

12.3.1 Home screening

If shown eligible on the online screening, participants will be contacted by a member of the research team to organise a face to face appointment at home. Prior to the home visit participants will be sent an Actiwatch 2, a painless watch-like device worn around the wrist to monitor sleep and wake cycles and activity patterns (body movement and ambient light). Accompanying the Actiwatch 2, participants will be sent and asked to fill out a sleep diary self-assessing their sleep whilst at home. Participants will be asked to wear the Actiwatch 2 and complete the sleep diary for at least 7 days before coming in to their face-face appointment.

At the face to face home screening the participant will have their hearing tested. Participants will go through various hearing tests (Section 12.4.3)

12.4 Neurotological assessment (Appendix E)

Neurotological testing will occur during the baseline, three and six month visits. Neurotological tests will be performed in a quiet room and therefore will not occur during any experimental noise conditions.

12.4.1 Examination

Participants will firstly be asked some questions regarding their clinical history that may affect the neurotological examination (e.g. Do you experience vertigo?). This will be followed by two tests. The matted Romberg test assesses a participant's ability to hold their balance whilst standing on a mat with their eyes closed. The second test, the Unterberger will require participants to walk on the spot with their eyes closed. This test will measure the angle of rotation from the line marked.

Clinical ear examinations (Otoscopy and Tympanometry) will also be performed prior to any tests to ensure that there is not any obstruction in the ear canals and determining eardrum function.

i) Otoscopy: Examines if there are any structural changes in the tympanic membrane and ear canal using a device called a otoscope.

ii) Tympanometry: A probe like device will be inserted into the ear canals and play a tone to measure the movement in the eardrum in response to changes in pressure caused by the tone.

